### 6.6.7 Procedure of Reporting Serious Adverse Events

- The Sponsor-Investigator primary responsibilities for safety reporting are to identify and follow-up on Serious Adverse Events (SAEs) experienced by participants in the study and to:
  - Evaluate and forward the information to the local regulatory authorities as required by local regulations
  - Forward to Merck/EMD Serono as required within the applicable contract executed between Merck/EMD Serono & the Sponsor-Investigator
- The following reportable events must be submitted to Merck within 2 business days or 3 calendar days (whichever comes first) using the applicable safety report form provided. The Principal Investigator(s) will assume responsibility for submitting the reportable event(s) to Merck as well as ensuring that any local

reporting requirements are completed in parallel.

- Serious Adverse Events (see section 6.6.2)
  - Exposure during Pregnancy or Breastfeeding (even if not associated with an adverse event)
  - Occupational exposure (even if not associated with an adverse event)
- Contact information for submission of reportable events to Merck:
  - [contact] or
  - E-mail: [name]
  - Specifying:
    - PROTOCOL Number and/or Title
    - Funder's Study Identifier
    - SUBJECT Number
    - Principal Investigator Name
    - Sponsor Name
    - SAE/ONSET DATE

#### **6.6.8 Monitoring of Subjects with Adverse Events**

- Any AE that occurs in the course of a clinical study must be monitored and followed up until the last study visit. It is the responsibility of the Investigator(s) that any necessary additional therapeutic measures and follow-up procedures are performed.

## 7 STATISTICS

### 7.1 Statistical Analysis

Objective response rate (ORR) will be expressed based on exact binomial distribution. Survival outcomes, including TTP, PFS, OS, and survival rate their corresponding 95% confidence interval, will be estimated using Kaplan-Meier method. The Fisher exact test will be used to correlate the binary clinical and biomarker data. The cut-off values of baseline and changes in the exo-PD-L1 and TGF- $\beta$ 1 levels will be calculated by the Receiver Operating Characteristic (ROC) curve analyses.

All of the reported P values will be 2-tailed, and P<0.05 will be considered statistically significant. No multiplicity will be considered. The analyses will be performed using statistical software packages SPSS and R.

**Procedures for Handling Missing, Unused, and Spurious Data:** All available data will be included in the data listings and tabulations. Where appropriate, imputations of values for missing data for primary and secondary efficacy analyses will be performed as specified in the Statistical Analysis Plan. All data recorded on the CRF will be included in the data listings that will accompany the clinical study report.

If, after the study has begun, but prior to the conduct of any analysis, changes made to primary and / or key secondary endpoints, or the statistical methods related to those hypotheses, then the protocol will be amended. Changes to exploratory analyses made after the protocol finalized will be documented and referenced in the final report. Post hoc exploratory analyses will also be identified in the final report.

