### 7.2 Sample Size Calculation

H0: The null hypothesis is that the overall response rate (ORR) is similar to historical result of immunotherapy, i.e. 20%

H1: The alternative hypothesis of treatment efficacy: experimental treatment with bintrafusp alfa would result in 40% ORR.

To detect 20% of differences from 20% to 40% in the number of patients proceeding to surgery, with Type I error of 0.05 and 80% power, the target sample size is 33 patients.

Modified Simon's two-stage optimal design will be used. In the first stage, 18 patients will be enrolled. If there are 4 or fewer responses in these 18 patients, the study will be stopped. Otherwise, 15 additional patients will be accrued for a total of 33 valid cases. The null hypothesis will be rejected if 11 or more responses are observed in 33 patients and the treatment will be considered worthy of further investigation. Patients may drop out before their objective response can be assessed. Such patients will be excluded for the ORR assessment and will be replaced by other patients that the objective response can be assessed. The study will be continued until the first or the second stage evaluation is achieved. Assuming 10% drop out rate, 38 patients will be accrued initially. We assume 50% of screened population will be eligible for the study, thus we plan to screen for 76 patients.

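### Protocol section 7.1 makes P values two-tailed at 0.05 and expresses ORR by the exact binomial, but section 7.2 rejects at 11/33 by a one-sided two-stage rule; at exactly 11 responses the two disagree

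*Protocol*

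**What the plan says.** Protocol section 7.1 gives one sentence on the primary endpoint: "Objective response rate (ORR) will be expressed based on exact binomial distribution". It then sets a general rule for tests: "All of the reported P values will be 2-tailed, and P<0.05 will be considered statistically significant". It names no separate test for ORR, gives no confidence level for the ORR interval, and does not refer to the two-stage design.

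Protocol section 7.2 takes 20% as the null response rate, and the alternative is that "experimental treatment with bintrafusp alfa would result in 40% ORR". The design is set "with Type I error of 0.05 and 80% power, the target sample size is 33 patients", with no sidedness stated. The sampling plan is two-stage: "Modified Simon's two-stage optimal design will be used". Stage 1 has 18 patients: "If there are 4 or fewer responses in these 18 patients, the study will be stopped". Otherwise 15 more are enrolled, and "The null hypothesis will be rejected if 11 or more responses are observed in 33 patients".

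No sentence says whether the count rule or the section 7.1 analysis decides the trial, or how the two fit together.

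**The concern.** The two sections describe different tests of the same hypothesis. Section 7.2 is a one-sided count rule whose error rate depends on the stage-1 stop. Section 7.1, read in the ordinary way, gives a two-tailed criterion and an exact binomial analysis of a single sample of 33. If both give the same answer at every possible count, the difference is only presentational. If they differ at the pass mark, the report could declare the null rejected beside an interval and a P value that do not exclude 20%, and the protocol would not say which prevails. Settling the conflict by quietly treating 12 responses as the threshold would cost power.

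**Working it through.** **Inputs (Protocol section 7.2).** Stage 1: n1 = 18, stop at 4 or fewer. Stage 2: 15 more, total 33. Reject at 11 or more. p0 = 0.20, p1 = 0.40, type I error 0.05, power 80%.

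**Step 1: reproduce the design.** The probability of a final count of at least r after continuing is

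R(p; r) = Σ over x = 5 to 18 of Bin(x; 18, p) × P(X2 ≥ r − x), with X2 ~ Bin(15, p).

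- R(0.20; 11) = 0.0458, the two-stage one-sided type I error.
- R(0.40; 11) = 0.8011, the power.

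The stated 0.05 and 80% are met, but 0.05 only one-sided: doubled, the error is 2 × 0.0458 = 0.092.

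**Step 2: ordinary exact binomial at the boundary, single sample of 33, null 20%.**

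| Count | 95% interval | 90% lower bound | Two-sided P (minimum likelihood / doubled) | One-sided P |
|---|---|---|---|---|
| 11 (33.3%) | 18.0% to 51.8% | 19.95% | 0.078 / 0.102 | 0.0508 |
| 12 (36.4%) | 20.4% to 54.9% | 22.5% | 0.027 / 0.043 | 0.0216 |

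At 11 every version fails to exclude 20%; at 12 every version excludes it. The conflict is confined to exactly 11 responses.

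**Step 3: separate the two causes at 11/33.**

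| | Two-sided at 0.05 | One-sided at 0.05 |
|---|---|---|
| Ordinary binomial | P 0.078 to 0.102; 95% interval from 18.0% | P 0.0508; 90% interval from 19.95% |
| Two-stage | P 0.092 (doubled); 95% interval 18.2% to 52.6% | P 0.0458; 90% interval 20.3% to 49.7% |

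The two-stage intervals invert R(p; r): the lower limit solves R(p; 11) = 0.05 and the upper limit solves 1 − R(p; 12) = 0.05, with 0.025 in place of 0.05 for the 95% interval.

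Only the bottom-right cell agrees with section 7.2. Changing sidedness alone moves P from about 0.08–0.10 to 0.0508, nearly all of the distance. Changing to the two-stage calculation alone leaves P at 0.092. The remaining one-sided gap, 0.0508 − 0.0458 = 0.0050, is the null probability of reaching 11 of 33 after 4 or fewer in the first 18, a path that the stage-1 stop removes.

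**Step 4: how often it matters.** P(final count exactly 11) = R(p; 11) − R(p; 12).

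- p = 0.40: 0.8011 − 0.7085 = 0.0926, or 9.3%.
- p = 0.35: 12.4%.
- p = 0.30: 11.6%.

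Requiring 12 instead would cut power at 40% from 80.1% to 70.9%.

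**Step 5: size of the estimation bias.** Over all outcomes, the raw proportion is biased by −1.5 points at a true ORR of 20%, −1.8 at 30% and −0.9 at 40%. At 11/33 the uniformly minimum variance unbiased estimator (UMVUE) is 35.3% against the raw 33.3%.

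**The case against.** The strongest reply is that section 7.1 promises neither an ORR P value nor an ORR confidence level, that two-stage intervals are also built from exact binomial probabilities, and that such detail belongs in an analysis plan that is not shown. The decision is already fixed by count in section 7.2, its error rate is within 0.05, and the conflict touches one count only.

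Much of this stands. The ORR interval and test are inferred from the ordinary meaning of an exact binomial expression of a proportion and from a rule covering all reported P values. No go/no-go decision, sample size or error rate of the count rule is wrong. What does not stand is leaving the matter to the analysis plan. The two-tailed rule is stated in the protocol without exception, and a test consistent with section 7.2 cannot satisfy it at 11/33, whichever exact method is used. Section 7.1 also calls for a protocol amendment if the statistical methods for the primary endpoint change, so the protocol is the place to settle it.

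Two stronger readings are tempting. One is that neglect of the two-stage design alone causes the clash. It does not: a two-stage analysis kept two-sided still conflicts (P about 0.092). The other is that the reported ORR would be materially biased and should be replaced by the UMVUE. The overall bias is under 2 points and downward, so it does not flatter the drug. The UMVUE is also not uniformly better: its root mean squared error at a true ORR of 20% is 0.091, against 0.079 for the raw proportion.

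**Conclusion.** The point holds as an inconsistency between sections 7.1 and 7.2. At exactly 11/33, section 7.2 rejects 20%, while the analysis that section 7.1 most naturally describes does not exclude it. The chance of that outcome is 9.3% at the design alternative and about 12% at a true ORR of 30% to 35%. Sidedness is the main cause and the ignored two-stage design the second; correcting either one alone leaves a disagreement.

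This assumes that the ORR result will carry an ordinary exact binomial interval or P value, and that the two-tailed rule applies to it as written. It does not show that the 11/33 rule is invalid: that rule keeps its one-sided error at 0.0458 and its power at 80.1%.

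**What to change.** In section 7.1, state that:

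- the count rule in section 7.2 governs the primary decision, at one-sided alpha 0.05;
- the primary ORR test is exempt from the two-tailed rule;
- ORR is reported with a one-sided P value and a two-sided 90% interval, both computed exactly from the two-stage sample space;
- the raw proportion is kept, optionally with the UMVUE beside it;
- any 95% interval is labelled descriptive, because at 11/33 it includes 20% even after two-stage adjustment.

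Section 7.2 should say that its 0.05 is one-sided.

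The cost is a few sentences and a few lines of R, with no change to sample size or conduct. The downside is that the primary endpoint then rests openly on a one-sided test and a less familiar interval.

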### **Rationale of Blocking TGF-B Pathway**

Despite the promising clinical activity, only 20% of NPC patients respond to anti-PD-1/PD-L1 therapies. Thus, there is an urgent need to improve objective response rates. One strategy is to combine anti-PD-L1/PD-1 with other immunotherapies, (23) as exemplified by the combination of anti-PD-1 and anti-CTLA-4, which has been approved for advanced melanoma. (24)

In normal physiology, the regulatory cytokine transforming growth factor- $\beta$  (TGF- $\beta$ ) functions to maintain immunological self-tolerance. (25-27) However, TGF- $\beta$  can promote tumor progression and facilitate tumor immune evasion through its effects on the innate and adaptive immune systems. The three TGF- $\beta$  isoforms, TGF- $\beta$ 1, TGF- $\beta$ 2, and TGF- $\beta$ 3 (25, 27), are highly expressed in many tumor types, and their serum concentrations correlate with poor clinical outcome. (27-29) TGF- $\beta$  functions as an autocrine or paracrine signal within the tumor microenvironment, where it promotes tumor progression via stromal modification, angiogenesis, and induction of epithelial-mesenchymal transition (EMT). (30-32) TGF- $\beta$  signaling in myeloid cells is also critical in driving metastasis. (33) In addition, TGF- $\beta$ 1 can directly inhibit T cell division and acquisition of effector function and natural killer (NK) cell function. (34-38) Furthermore, because the up-regulation of TGF- $\beta$  signaling-associated genes has been linked to anti-PD-1 resistance, blockade of TGF- $\beta$  signaling may target mechanisms of resistance and sensitize tumors to anti-PD-1/PD-L1 therapies. (39)

In NPC patients, high levels of TGF- $\beta$ 1 are positively correlated with disease stage. (40) Up-regulation of TGF- $\beta$  pathway is associated with aggressive phenotype of NPC by inducing EMT, that ZEB1/2 genes, Flot1/2, human high mobility group A2 (HMGA2) are the possible mediators. (41-44) Furthermore, a recent report found that miR-449b, a miRNA strongly associated with NPC distant metastasis, activates of the TGF- $\beta$  pathway, which subsequently induces Cisplatin resistance in NPC through the PTEN/AKT pathway. (45)

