**(d) Immune Markers**

Flow cytometry analyses revealed that, bintrafusp alfa increased the density of CD8+ tumor-infiltrating lymphocytes (TIL), tumor-infiltrating NK cells (TINKs), tumor-associated dendritic cells (TADCs), tumor-associated monocytes, but significantly decreased the density of tumor-associated neutrophils (TANs) and PD-1+ tumor-associated macrophage (TAM). Further analysis by immune cell depletion studies shown that the anti-tumor activity of bintrafusp alfa was mainly mediated by CD8+ T-cells and NK cells. Also, RNA sequencing has demonstrated that bintrafusp alfa promotes the expression of immune cell signature genes (69).

There are also recent findings suggest that exosomal PD-L1 plays an important role by causing immuno-suppression in melanoma and breast cancer. (70-71) High level of circulating exosomal PD-L1 pre-anti-PD-1 treatment may reflect the “exhaustion” of T-cells, while an increase in the level of circulating exosomal PD-L1 after anti-PD-1 treatment may reflect re-invigoration of T-cell activity against melanoma. So exosomal PD-L1 may be a sensitive marker to predict response check-point inhibitor immunotherapy.

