## **6 FOLLOW UP AND OUTCOME EVALUATION**

### **6.1 Follow-Up Schedule**

All participants will be followed every 2 weeks during the intervention. At each visit, patient's performance status and toxicity of treatment will be monitored, and blood test will be checked for complete blood count, liver function, and renal function. Thyroid function test and early morning cortisol (9am) will be performed at least every 4 weeks while on bintrafusp alfa therapy. For female patients in reproductive age, urine or serum pregnancy test needs to be performed at least every month while the subject is on bintrafusp alfa therapy. All adverse events and laboratory abnormalities will be graded per the National Cancer Institute Common Terminology Criteria for Adverse Events, version 4.0.

For blood-borne immune markers and exploratory biomarkers, plasma EBV DNA will be determined before treatment and every 2 weeks until disease progression; plasma TGF $\beta$ 1 measurement will be performed every 8 weeks until disease progression; exo-PD-L1 concentration will be measured every 2 weeks until disease progression.

Tumor imaging by CT head, neck, chest, abdomen, and pelvis will be done at baseline, every 8 weeks for the first 12 months, then every 12 weeks thereafter. Response will be assessed per RECIST version 1.1. Treatment decisions will be based on Investigator(s) review.

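### Section 7.1 lets ROC-derived marker cut-offs fall under the general P<0.05 rule; read naturally, this calls a useless marker significant in about 7–11% or 14–22% of trials that reach 33 patients

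*Protocol*

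**What the plan says.** Protocol section 7.1 contains three statements that bear on this.

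- Association test: "The Fisher exact test will be used to correlate the binary clinical and biomarker data".
- Cut-offs: the next sentence opens with "The cut-off values of baseline and changes in the exo-PD-L1", adds TGF-β1, and says the values are obtained by ROC curve analysis.
- Significance: "All of the reported P values will be 2-tailed, and P<0.05 will be considered statistically significant". The same paragraph declines any multiplicity adjustment.

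On exploratory work, section 7.1 covers changes and post hoc analyses: "Changes to exploratory analyses made after the protocol finalized will be documented and referenced in the final report". It does not take planned exploratory tests out of the P<0.05 rule.

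Exploratory objectives 2 and 3 (section 2.3) relate response, PFS and OS to TGF-β1 and to exosomal PD-L1. Both markers are sampled on treatment; in section 6.1, "exo-PD-L1 concentration will be measured every 2 weeks until disease progression". The Background, part (d), gives the motive: "So exosomal PD-L1 may be a sensitive marker to predict response check-point inhibitor immunotherapy".

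**The concern.** A ROC cut-off is chosen because it separates responders from non-responders. Fisher's exact test takes the two marker groups as settled before the outcomes are seen. If the split is searched for and then tested in the same patients, the P value ignores the search and is too small. The apparent sensitivity and specificity are flattered in the same way.

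A marker with no information would then be reported as statistically significant more often than the 5% a reader will assume, and might be carried into later studies on that basis. The question is how much more often in a trial of this size, given its stopping rule.

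**Working it through.** **Inputs from section 7.2.** Response rate 20% under the null and 40% under the alternative; stop if 4 or fewer of 18 respond; otherwise 33 evaluable patients, with success at 11 or more. From section 7.1: two-sided P<0.05.

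**The plan's own figures.** The exact two-stage binomial calculation gives type I error 0.0458 and power 0.8011, matching the stated 0.05 and 80%. The plan gives no separate error rate for the marker tests.

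**Assumptions.** Cut-off derived in the trial's patients; response as the ROC outcome; marker independent of response; no ties. Two ROC criteria are tried: the Youden index (largest sensitivity + specificity − 1) and the ROC point closest to perfect classification ('corner'). Direction is either fixed in advance or taken from the data (AUC above or below one half).

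**Method.** For each responder count, put responders in random order along the marker (100,000 orderings at n=33), choose the cut-off, and apply Fisher's test. Only ranks matter, so no marker distribution is assumed.

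**Percentage with P<0.05, n=33, useless marker, by number of responders**

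| | 7 | 8 | 9 | 10 | 11 | 12 | 13 |
|---|---|---|---|---|---|---|---|
| Youden, direction fixed | 10.5 | 11.2 | 10.5 | 10.2 | 10.5 | 11.4 | 10.1 |
| Corner, direction fixed | 7.6 | 8.9 | 7.4 | 7.0 | 6.5 | 6.2 | 6.7 |
| Youden, direction from data | 20.0 | 22.3 | 20.7 | 20.1 | 20.4 | 21.7 | 20.1 |
| Corner, direction from data | 14.5 | 17.7 | 14.7 | 14.0 | 12.7 | 12.1 | 13.4 |
| Fisher at pre-set median split | 3.9 | 3.9 | 1.7 | 2.6 | 2.6 | 3.2 | 3.2 |

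The rank-sum test gives 4.5–4.9%. Fisher at a pre-set split stays below 5%, so the excess comes from the search.

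**Averaged over responder counts, at true response rates of 20 / 30 / 40%**

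| | Stage 2 reached | All trials, including those stopped at 18 |
|---|---|---|
| Youden, fixed | 10.4 / 10.7 / 11.1 | 6.5 / 9.2 / 10.7 |
| Corner, fixed | 7.5 / 7.0 / 7.0 | 5.5 / 6.6 / 6.9 |
| Youden, from data | 20.5 / 20.9 / 21.6 | 12.9 / 18.0 / 20.9 |
| Corner, from data | 14.7 / 13.9 / 13.7 | 11.0 / 13.0 / 13.6 |

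**How the second column arises** (response rate 20%, Youden, direction fixed). In stage 1, P(0 or 1 responder) = 0.099, P(2) = 0.172, P(3) = 0.230 and P(4) = 0.215, so the trial stops with probability 0.716. With one responder in 18 the smallest possible P is 1/18 = 0.056, so 0 or 1 responder contributes nothing. The rates at 2, 3 and 4 responders are 0.040, 0.055 and 0.073.

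- Stopped: 0.172×0.040 + 0.230×0.055 + 0.215×0.073 = 0.035
- Continued: 0.284 × 0.104 = 0.030
- Total: 0.065

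Among stopped trials alone the rate is 0.035/0.716 = 4.9%, so they show no excess in this case.

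**Optimism.** With 10 responders of 33, Youden and direction fixed, a useless marker shows mean sensitivity 64% and specificity 57%: 0.64 + 0.57 − 1 = 0.21, where the true value is 0.

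**The case against.** **The procedure is inferred.** Three links are unstated: that the cut-offs come from this trial's patients, that response is the ROC outcome, and that the split markers go into Fisher's test. The last is the weakest. The Fisher sentence precedes the ROC sentence, and tissue PD-L1 or plasma EBV DNA could supply binary data without a ROC search. The cut-offs might instead form groups for PFS and OS. This stands as a limit on the claim. Still, no other source of cut-offs is named, Fisher's is the only association test named, and section 2.3 puts response first among the outcomes. The reading is natural, but a reader should not infer that the protocol prescribes this sequence in terms.

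**The larger range may not apply.** The Background suggests directions: "an increase in the level of circulating exosomal PD-L1 after anti-PD-1 treatment may reflect re-invigoration of T-cell activity against melanoma", and for the TGF-β isoforms, "their serum concentrations correlate with poor clinical outcome". If these are adopted in advance, the lower range applies. The protocol does not commit to them.

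**Trials that stop early dilute the effect.** This stands: at a 20% response rate with direction fixed, the overall rate is only 5.5–6.5%.

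**It is exploratory, and the SAP may deal with it.** The ROC criterion, the direction and any resampling can properly be left to the SAP. But the significance rule in section 7.1 covers all reported P values, with no exploratory exception. Declining multiplicity adjustment concerns several tests; it does not disclose that a single test is biased by its own cut-off search.

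**Conclusion.** The point holds in conditional form and at minor priority. On the natural reading, the error rate per marker variable once stage 2 is reached is about 7–11% with direction fixed and about 14–22% with direction from the data, against a nominal 5%. Over all trials, at true response rates of 20–40%, it is about 5–11% and 11–21%. Where a value falls depends on the ROC criterion, the responder count and whether the trial continues past 18 patients.

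A reader might infer that the trial's main conclusion is at risk. It is not: the rule of 11 or more responses in 33 uses no marker. Nor do these figures cover PFS or OS, which were not examined, or the overall error across several markers, where the protocol openly declines adjustment. What needs correcting is that section 7.1 allows an unadjusted P value at a searched cut-off to be called statistically significant.

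**What to change.** Add to section 7.1:

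- ROC-derived cut-offs are hypothesis-generating, and an unadjusted P<0.05 at such a cut-off is not called statistically significant. This sentence alone removes the misstatement.
- Each marker is tested against response as a continuous variable (rank-sum test, AUC with 95% confidence interval), or a permutation P value that repeats the cut-off search is given.
- Fisher's exact test is kept for variables that are binary by a definition fixed in advance.

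The cost is a few lines of text, a short script and fewer nominally significant marker results; no extra patients, samples or visits. To show the trade-off, assume a normally distributed marker with true AUC 0.75 and 10 responders of 33. The searched Fisher test (Youden, direction fixed) is significant in 80% of trials, but at a true error rate of about 10%. With error held near 5%, the permutation test detects the marker in 68% and the rank-sum test in 65%. Fisher at a pre-set median split detects it in 48%.

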### **Study Hypothesis**

Based on the above findings, we hypothesize that bintrafusp alfa offers better response rate than historical results by anti-PD-1/ anti-PD L1 therapy in previously platinum treated recurrent or metastatic NPC patients.

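### Does the 2-tailed P value sentence in section 7.1 conflict with the one-sided 11-of-33 success rule in section 7.2?

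*Protocol*

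**What the plan says.** The protocol sets the primary test in section 7.2. The null ORR is 20%, and the alternative is that "experimental treatment with bintrafusp alfa would result in 40% ORR". The size is justified "with Type I error of 0.05 and 80% power, the target sample size is 33 patients". A Simon two-stage design follows. The first 18 patients are assessed, and the trial stops if 4 or fewer respond. Otherwise 15 more are added, and "The null hypothesis will be rejected if 11 or more responses are observed in 33 patients". The section does not say whether the 0.05 is one- or two-sided.

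Section 7.1 covers analysis in general. On the primary endpoint it says only that "Objective response rate (ORR) will be expressed based on exact binomial distribution". After naming the Kaplan-Meier, Fisher exact and ROC methods for the other outcomes and the biomarkers, it adds that "All of the reported P values will be 2-tailed, and P<0.05 will be considered statistically significant". It states no exception for ORR.

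The Study Hypothesis at the end of section 1 is directional: "bintrafusp alfa offers better response rate than historical results".

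**The concern.** Read side by side, the two sections seem to set different standards for the primary endpoint. Section 7.1 applies a 2-tailed 0.05 threshold to every reported P value. The boundary in section 7.2 reaches its stated error rates only if the whole 0.05 lies in the upper tail. With exactly 11 responses in 33 patients, a report could reject the null under 7.2 and print beside it an ORR P value that 7.1 labels not significant.

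If the 2-tailed sentence were taken to govern the primary test, the boundary would have to move to 12 of 33. Power at 40% would then be 0.709, short of the stated 80%. Which sentence governs would also have to be settled after the data were known, at the very result where the choice matters.

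**Working it through.** **Inputs (protocol section 7.2).** Null rate 0.20; alternative 0.40; first stage 18 patients, continue at 5 or more responses; second stage 15 patients; reject at 11 or more of 33; stated type I error 0.05 and power 80%.

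**Step 1: the plan's own figures.** With X1 the first-stage and X2 the second-stage responses, the probability of rejecting at true rate p is

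P(reject) = sum over x = 5 to 18 of P(X1 = x; 18, p) × P(X2 ≥ 11 − x; 15, p).

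| x | Product at p = 0.20 | Product at p = 0.40 |
|---|---|---|
| 5 | 0.1507 × 0.0611 = 0.0092 | 0.1146 × 0.5968 = 0.0684 |
| 6 | 0.0816 × 0.1642 = 0.0134 | 0.1655 × 0.7827 = 0.1296 |
| 7 | 0.0350 × 0.3518 = 0.0123 | 0.1892 × 0.9095 = 0.1720 |
| 8 | 0.0120 × 0.6020 = 0.0072 | 0.1734 × 0.9729 = 0.1687 |
| 9 | 0.0033 × 0.8329 = 0.0028 | 0.1284 × 0.9948 = 0.1278 |
| 10 | 0.0008 × 0.9648 = 0.0007 | 0.0771 × 0.9995 = 0.0770 |
| 11 or more | 0.0002 | 0.0576 |
| **Total** | **0.0458** | **0.8011** |

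(Products use unrounded factors.) The stated 0.05 and 80% are reproduced as a one-sided test. They do not hold for a two-sided 0.05 test, because 0.0458 exceeds 0.025.

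**Step 2: where a 2-tailed P value would disagree.** Exact P values against 20%:

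| Responses of 33 | Section 7.2 | Minimum-likelihood P | Doubled single-stage tail | Doubled two-stage tail |
|---|---|---|---|---|
| 10 | do not reject | 0.188 | 0.214 | 0.177 |
| 11 | reject | 0.078 | 0.102 | 0.092 |
| 12 | reject | 0.027 | 0.043 | 0.041 |

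At 11 of 33 the single-stage upper tail is 0.0508, and 2 × 0.0508 = 0.102. The minimum-likelihood value adds the lower-tail outcomes (0 to 2 responses) that are no more likely than 11: 0.0508 + 0.0268 = 0.078. For the two-stage version, 2 × 0.0458 = 0.092.

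Among final results of 10, 11 and 12, only 11 gives different answers. Below 10, section 7.2 does not reject; above 12, both standards reject.

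**Step 3: how often that result occurs.** P(X1 ≥ 5 and X1 + X2 = 11) is 0.093 at a true ORR of 40% and 0.116 at 30%.

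**Step 4: the alternative boundary.** With the same first stage and a cut of 12 of 33, the formula gives 0.0205 at 20% and 0.709 at 40%. No sentence in the protocol sets this cut.

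**The case for a change.** The best case for acting is that the word "all" in section 7.1 admits no exception. Section 7.2 poses a formal hypothesis test, and a P value for the primary endpoint is something a report may well contain. One-sided intent has to be inferred, whereas the 2-tailed rule is explicit. Section 7.1 itself requires a protocol amendment if the methods for the primary hypotheses change, and two clarifying sentences written beforehand would cost nothing. Adding them after seeing 11 of 33 would look like fitting the rule to the result.

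The facts in this case are right: section 7.2 gives no sidedness, section 7.1 gives no exemption, and the two would read awkwardly together at 11 of 33. The consequence does not follow.

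- The 2-tailed sentence governs P values that are reported, and the plan calls for none on ORR. The primary decision is a count.
- The direction is plain from the design: the alternative is above the null, the interim rule stops only for too few responses, and the final rule rejects only for many.
- The power of 0.709 needs a boundary of 12, while section 7.2 states 11.
- A related argument is that a plain single-stage calculation at 11 of 33 gives a one-sided P of 0.0508 and a 90% lower limit of 19.95%, just missing the null even after a one-sided label is added. Section 7.2 does not base its decision on either quantity. Interval level and two-stage adjustment are normally left to the statistical analysis plan, which section 7.1 mentions and which was not available here.

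**Conclusion.** No change to the plan is called for. Followed as written, section 7.2 gives a decision with exact type I error 0.0458 and power 0.801, which is what it claims. Labelling the test one-sided would leave the sample size, boundary, error rates and conclusion as they are.

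What remains is an unstated label that an analyst will supply correctly from the design. The visible effect is limited to one result, exactly 11 of 33. Its probability is 9.3% at a true ORR of 40% and 11.6% at 30%, and it matters only if an optional 2-tailed P value is printed. The worst outcome is an awkward sentence in the report, with the conclusion that the treatment merits further study unaltered.

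This rests on two readings: that the explicit count rule takes precedence over a general sentence on reported P values, and that expressing ORR by the exact binomial distribution means estimating it rather than testing it a second time. The error rates also assume 33 assessable patients, as section 7.2 intends by replacing those who cannot be assessed.
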